Lacosamide is well-tolerated and has no known drug-drug interactions. In controlled clinical trials, the rate of discontinuation as a result of an adverse event was 8% and 17% in patients randomized to receive lacosamide at the recommended doses of 200 and 400 mg/day, respectively, 29% at 600 mg/day, and 5% in patients randomized to receive placebo. The adverse events most commonly leading to discontinuation were dizziness, ataxia, vomiting, diplopia, nausea, vertigo, and vision blurred. Abnormalities in liver function tests have been observed in controlled trials with lacosamide in adult patients with partial-onset seizures who were taking 1 to 3 concomitant AEDs. Elevations of ALT to $\geq 3 \times$ the upper limit of normal (ULN) occurred in 0.7% (7/935) of lacosamide patients and 0% (0/356) of placebo patients. One case of hepatitis with transaminases $> 20 \times$ ULN was observed in one healthy subject 10 days after lacosamide treatment completion, along

with nephritis (proteinuria and urine casts). Serologic studies were negative for viral hepatitis. Transaminases returned to normal within one month without specific treatment. At the time of this event, bilirubin was normal. The hepatitis/nephritis was interpreted as a delayed hypersensitivity reaction to lacosamide.

A list of possible adverse events is provided in Section 3.12. This includes events reported by patients treated with lacosamide in all clinical trials in patients with partial-onset seizures, including controlled trials and long-term open-label extension trials, as well as events identified during post approval use of lacosamide. Because the latter are reported voluntarily from a population of uncertain size, it is not always possible to reliably estimate their frequency or establish a causal relationship to drug exposure. The most frequently reported adverse events include dizziness, vertigo, diplopia, blurred vision, nystagmus nausea/vomiting, diarrhea, fatigue, headache, somnolence, tremor, ataxia, and imbalance. Post approval adverse events of potential significance include bradycardia and rash.

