8.0 EVALUATION DURING STUDY

General Requirements

Unless otherwise noted, all evaluations may be performed within 14 days before the scheduled date. A model study calendar is presented in Figure 8-1.

- 8.1 Laboratory tests will be obtained only as deemed necessary by the investigator during study treatment.
- 8.2 All relevant information regarding drugs, doses, laboratory examinations, and treatment-related toxicities shall be documented in the patient's medical record and flow sheets.
- 8.3 A complete history and neurologic exam (to include vital signs and documentation of the patient's Karnofsky Performance Status) will be performed at least every 3 months, +/-2 weeks.
- 8.4 Every 4 weeks when the patient is not seen by the study team, telephone contact between the patient and a study clinician (nurse or MD) is required to assess for possible seizure in the preceding month.. The Site to complete the BTTC 11-01 Interim Telephone Contact Checklistform . Calls or visits must occur on the scheduled date or within 2 weeks prior to the scheduled date.
- 8.5 *EEG should be obtained whenever possible to confirm the clinical impression of seizure.* Because the diagnosis of seizure is frequently made by history, this test is optional.
- 8.6 All patients will be followed for overall survival at least every 3 months, when possible. The follow up will continue until 5 years after the End of Study visit. The follow up can take place via telephone contact by the nurse, study coordinator, or MD.
- 8.7 The MDASI-BT (Appendix 17.3) will be administered every 4 weeks in clinic or by telephone *ONLY* by the nurse or MD.
- 8.8 All patients will be evaluated for adverse events at the monthly telephone calls or visits. In addition all serious adverse events will be reported to the OMCR and the study chair as directed in section 15.7.

Figure 8-1. Model Study Calendar.

	Screening	Start of treatment Visit 1^c (Day 1 of Month 1)	On-treatment period Visits 2-4^c (Day 1 of Months 4, 7, 10)	Last treatment visit Visit 5^c (Day 1 of Month 13)
Demographic data	X			
Drug dispensing/return		X	X	X
Re-Order Drug			X^e	
MDASI-BT ^a		X	X	X
Karnofsky Performance Status	X	X	X	X
EKG ^b	X			
Lab tests ^b	X	X		
EEG ^d	X			
Medical and seizure history	X	X	X	X
Physical and neurologic examination	X	X	X	X
Randomization		X		
Recording of adverse events ^a			X	X
Verification of inclusion/ exclusion criteria	X			
Vital signs	X	X	X	X
Written informed consent	X			

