Based on this simulation program, the maximum fixed sample size to be accrued is 298 patients. The power for this analysis is 83.6% (power based on 1000 simulations). Because we plan 1 interim analysis using an O'Brien-Fleming stopping rule, we will need to adjust the sample size upward using the group sequential-to-fixed sample size ratio of 1.008 [35]. While this ratio is exact for trials with 80% power, it is a conservative lower bound for trials with greater than 80% power [35]. This ratio results in a trial with 302 patients (i.e., the largest even integer greater than 298×1.008). This results in a trial with 151 patients randomized to L and 151 patients randomized to P. The primary measure of efficacy is time to first seizure (TFS). The primary test of the difference in TFS between the treatment arms will be based on the likelihood ratio statistic for the treatment effect in a stratified proportional hazards regression model with anticonvulsant use as the stratification factor. The MDACC DSMB will periodically meet (either once every 6 months or annually) to evaluate safety and efficacy. The interim analysis will take place after 21 events have been observed. We will assess efficacy using an O'Brien-Fleming stopping rule with a nominal critical value of 2.7959 at the interim analysis. A futility analysis based on a conditional power assessment may be performed if the hazard ratio between the two treatment arms is approximately 1. If a conditional power assessment is performed and the conditional power is less than 0.10 the trial will be stopped for futility. The decision to perform this futility analysis will include an assessment of the number of events observed (i.e., at least 50% of the expected 42 events have occurred and all patients have not yet enrolled in the trial). If the study continues to full accrual, the final analysis will take place when all of the patients have either been followed for 1 year or have experienced a seizure event. We will test the null hypothesis $HR=1.00$ against $HR \neq 1.00$ at the 0.05 level. The conditional power for the time-to-event outcome will be computed based on the method described in Design and Analysis of Clinical Trials with Time-to-Event Endpoints (Peace 2009, page 60) and Lan Simon and Halperin (1982).

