15.12. Guidelines and Procedure for Unblinding Treatment

The site/treating Principal Investigator may request unblind the patient's treatment under certain circumstances:

- (1) A life –threatening event;
- (2) protocol-defined seizure activity;
- (3) An AE that is concerning to the site Primary Investigator
- (4) At the time study treatment is discontinued.

The unblinding procedure is outlined below. All parties must strictly adhere to the procedure in order to maintain protocol integrity.

1. The treating physician will call and email [name] and/or his back up to request the unblinding.
2. The treating physician completes the Unblinding Request form:
3. The treating physician will sign and date the completed request form.
4. The treating physician will scan and e-mail the completed unblinding request form to [name] or designee and cc MDA Anderson OMCR BTTC Staff ([contact])
5. If [name], or his back-up, approves the unblinding, he will sign, date, scan, and email the Unblinding Request form to the study statistician, [name], [name] back-up, and cc the M.D. Anderson OMCR and the requesting physician.
6. [name], and/or his back-up, will unblind the patient, and email **the treatment assignment to the treating physician only**. [name] will follow up by sending the completed patient unblinding notification memo to the requesting physician.
7. The treating physician will document the unblinding request and outcome in the patient's chart following their institution's policy and procedures **within 24 hours of the unblinding.**
8. The OMCR will notify the MDA IRB and the MD Anderson DSMB of routine patient unblindings at the time of the annual protocol approval. The OMCR will notify the DSMB of each emergency unblinding as they occur.
9. All research staff involved in the activity for this protocol should continue to remain blinded to drug assignment/randomization.
10. If the unblinded patient experienced an SAE, the SAE is to be processed per the protocol, BTTC Operation's Manual, and the institution's policy and procedure. Patient will be taken off treatment and followed for 30 days after last dose or until the event has been resolved.

Contact Information:

NAME	PHONE NUMBER	EMAIL ADDRESS
- [name]. (study chair)	[contact]	[contact]
[name], M/D. ([name] back-up)		
[name]. (study biostatistician)	[contact]	[contact]
[name] (1st back up to [name])	[contact]	[contact]
[name] (2nd back up for [name])	[contact]	[contact]

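### Section 15.12 ground (4) permits routine unblinding of patients who stop drug early without a seizure and are still at risk for the primary endpoint; the likely effect on the hazard ratio is small, but one clause would close the gap

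*Combined protocol and SAP*

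**What the plan says.** Section 15.12 lists four grounds on which the site investigator may ask for a patient's assignment: a life-threatening event, protocol-defined seizure, an adverse event of concern to the investigator, and "4) At the time study treatment is discontinued". The fourth carries no further condition. Step 8 distinguishes routine from emergency unblinding, so non-urgent use is expected.

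The same section sets limits. Each request needs approval from the study chair or back-up (roles taken from the contact table), who then "approves the unblinding, he will sign, date, scan, and email the Unblinding Request form to the study statistician". The statistician's side sends "the treatment assignment to the treating physician only". Step 9 adds: "All research staff involved in the activity for this protocol should continue to remain blinded to drug assignment/randomization". Under step 7, however, "The treating physician will document the unblinding request and outcome in the patient's chart".

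Section 10.1 lists several reasons for stopping treatment that are not seizures: toxicity, voluntary withdrawal, intercurrent illness and pregnancy. Stopping does not close the primary endpoint. Section 11.1 states that "the final analysis will take place when all of the patients have either been followed for 1 year or have experienced a seizure event", and the ITT rule in 11.2.1 drops no data from the first dosing date on. Between visits, 8.4 says that every 4 weeks "telephone contact between the patient and a study clinician (nurse or MD) is required to assess for possible seizure in the preceding month". Section 9.2 gives classification to a blinded committee working from forwarded medical records.

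**The concern.** For a patient who stops early and seizure-free, ground (4) allows the assignment to be disclosed while the primary endpoint is still open. Two routes then lead to the endpoint.

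- **The treating physician.** Section 9.1 leaves it to this person to deem certain attacks non-neurologic and so excluded. Section 8.5 notes that seizure is often diagnosed by history and makes EEG optional, so judgement matters. The one person who is told the arm is a person with a say in what counts.
- **The chart.** Site staff who make the seizure contacts may read it, and medical records are what the committee receives. No redaction is described.

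Exposure may also differ by arm. Section 2.5 reports that "the rate of discontinuation as a result of an adverse event was 8% and 17% in patients randomized to receive lacosamide" at 200 and 400 mg/day respectively, against 5% on placebo. If knowledge of the arm changes how readily a spell is reported, worked up or forwarded, the hazard ratio moves for reasons unrelated to assigned treatment. Blinding lost during follow-up cannot be restored at analysis.

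**Working it through.** **The plan's own figures.** From 11.1, one-year risks of 20% (placebo) and 8% (lacosamide) under exponential times give hazards −ln(0.80) = 0.2231 and −ln(0.92) = 0.0834. Their ratio is 0.374, as stated. The stated 42 events is 151 × (0.20 + 0.08) = 42.3, which allows for no loss to follow-up. Simulating the fixed design (298 patients, exponential loss of 15% by one year, 10,000 runs) gives power of 83.5% against the stated 83.6%. These figures are not in dispute.

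**Assumptions.** The documents give no stopping rates for this trial. I take the epilepsy-trial rates for stopping because of adverse events: 17% at 400 mg/day, the daily total of the target dose in 6.2.1.4, and 5% on placebo. Stop times are uniform over the year, risk returns to the placebo hazard once lacosamide stops, and loss has hazard −ln(0.85) = 0.1625. Every stopper is assumed unblinded, which is an upper bound.

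**Patients who stop.** 151 × 0.17 = 25.7 and 151 × 0.05 = 7.6. With lacosamide rates from 8% (200 mg/day) to 23.8% (section 2.3, AED change or discontinuation in brain tumor patients), the first figure runs from 12 to 36.

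**Events after stopping.** For a stopper with on-drug hazard h, the chance of a recorded first seizure after stopping is

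0.2231/(0.2231 + 0.1625) × ∫₀¹ e^(−(h+0.1625)s) [1 − e^(−0.3857(1−s))] ds.

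- Lacosamide (h = 0.0834): 0.5786 × (0.8866 − 0.7298) = 0.0907; × 25.7 = 2.3 events.
- Placebo (h = 0.2231): 0.5786 × (0.8297 − 0.6800) = 0.0866; × 7.55 = 0.65 events.

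**Total events, with loss.**

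- Placebo: 151 × 0.5786 × (1 − e^(−0.3857)) = 28.0.
- Lacosamide without stopping: 151 × 0.3391 × (1 − e^(−0.2459)) = 11.2. Stopping adds 2.33 at the placebo hazard and removes the 0.91 that would have occurred at the drug hazard, giving 12.6.
- Together 40.5. About 3 of roughly 41 events fall after stopping: 2.3/12.6 = 18% of lacosamide events and 0.65/28.0 = 2% of placebo events.

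**Hazard ratio** (Cox model, 1,000,000 simulated patients per arm):

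| Scenario | HR |
|---|---|
| No stopping | 0.374 |
| Stopping, full and even reporting, no other AED | 0.42 |
| As above, 30% of lacosamide after-stop events unreported | 0.40 |
| Only lacosamide stoppers receive an equally effective AED | 0.37 |
| Only placebo stoppers do | 0.43 |

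The step from 0.374 to 0.42 is the effect of stopping drug and would occur under perfect blinding. Only the later rows concern unblinding. Losing 30% of 2.3 events is 0.7 of an event. If a quarter of stoppers are affected, the figures are about 0.416 for under-reporting and 0.411 to 0.425 for AED use.

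For comparison, the standard error of the log hazard ratio is about √(1/12.6 + 1/28.0) = 0.34. The shift from 0.42 to 0.40 is ln(0.42/0.40) = 0.05, about one seventh of that.

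**Other stopping rates.** At 8% on lacosamide, after-stop events fall to 2.3 × 8/17 = 1.1. Adding an assumed further 13% in each arm (30% v 18%) gives 0.46, with a range of 0.37 to 0.49.

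**The case against.** A reader might infer that follow-up after ground (4) is run by people who know the arm. The documents do not support that. Unblinding must be requested and approved, only the treating physician is told, other research staff are to stay blinded, and a nurse may make the seizure contact. Two independent neurologists with no other study role classify each event, and a third settles disagreement. These safeguards are real. They remain incomplete because no approval criteria are given, the one person told has a role under 9.1, and nothing shields the chart or the records sent to the committee.

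A reader might also take 17% v 5% as the imbalance that ground (4) creates. Those are stops for adverse events, and most such patients could be unblinded under ground (3) anyway. What ground (4) adds is mainly stops for other reasons, for which the documents give no rate and no arm difference. This point stands, so a fix confined to ground (4) would miss most of the patients counted above.

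Three further points stand in part.

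- Ground (4) is not purely elective: pregnancy requires stopping and does not clearly fit grounds (1) to (3).
- The AED scenarios are bounds. They assume that all stoppers in one arm and none in the other are treated. They also assume that the 6.1.2d restriction, worded as applying on study, lapses with treatment; section 15.5 separates off treatment from off study.
- Seizure contact after stopping is not fully explicit. Section 8.4 has no on-treatment limit, but calendar footnote a limits the MDASI-BT and adverse-event calls to the treatment period. If scheduled contact lapses, ascertainment leans more on patient reports and the treating physician.

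**Conclusion.** The gap is in the text: ground (4) permits non-emergency unblinding of a seizure-free patient who is still at risk for the primary endpoint, and no section restricts it. The treating physician may then know the arm for the rest of the year, and the chart entry may reveal it to others.

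The size is modest. Under the assumptions above, about 3 of roughly 41 events are exposed, and plausible shifts attributable to unblinding are a few hundredths or less on the hazard ratio. This rests on borrowed stopping rates and on all stoppers being unblinded. The exposure is mainly in the ITT analysis, since the per-protocol set drops data later than 30 days after stopping. The stated power is unaffected. The point does not threaten the trial's conclusion, but it is an avoidable source of bias with a cheap remedy.

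**What to change.** - Limit routine unblinding under ground (4) to patients whose primary endpoint is closed: first seizure submitted to the event committee, or one-year seizure contact completed. Leave grounds (1) to (3), and any unblinding needed for patient care, such as in pregnancy, available.
- For anyone unblinded on any ground while still at risk, have a nurse or MD who is still blinded make the remaining 8.4 seizure contacts. State in 8.4 whether those contacts continue after treatment stops.
- Keep the assignment out of all records sent to the event committee.
- Record the date and reason of each unblinding, and report counts by arm.
- Optionally, repeat the primary Cox analysis censoring at unblinding, as a sensitivity analysis only. Such censoring may be informative, so it does not isolate ascertainment bias.

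The cost is a qualifying clause in 15.12, a redaction step and some record-keeping. The downside is that non-urgent disclosure for early stoppers waits until the endpoint is closed.

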This study will utilize the CTCAE version 4.0 for Toxicity and Adverse Event reporting. A copy of the CTCAE version 4.0 can be downloaded at http://ctep.cancer.gov/protocolDevelopment/electronic_applications/ctc.htm

17.2 **Karnofsky Performance Status and Neurological Exam**

[figure not shown]
Patient's performance status and Neurologic Exam will be graded according to the following scales:

Karnofsky Performance Status

KPS 100	Normal; no complaints; no evidence of disease
KPS 90	Able to carry on normal activity; minor signs or symptoms of disease
KPS 80	Normal activity with effort; some sign or symptoms of disease
KPS 70	Cares for self; unable to carry on normal activity or do active work
KPS 60	Requires occasional assistance, but is able to care for most personal needs
KPS 50	Requires considerable assistance and frequent medical care
KPS 40	Disabled; requires special care and assistance
KPS 30	Severely disabled; hospitalization is indicated, although death no imminent
KPS 20	Very sick; hospitalization necessary; active support treatment is necessary
KPS 10	Moribund; fatal processes progressing rapidly
KPS 0	Dead

17.3 MD Anderson Symptom Inventory for Brain Tumors (MDASI-BT)

(The MDASI – BT is created by the OMCR programming staff upon request for each protocol. The standard MDASI – BT questionnaire is used as a template. This form will contain coding “landmarks” that enable the data to be scanned into the MDACC data repository for MDASI results. Please contact the OMCR to obtain the questionnaire that is to be attached to the protocol.)

Date: / /
(month) (day) (Year)

Participant's Initials:

PLEASE USE A BLACK INK PEN BTTC 11-01 Patient #:

[figure not shown]
MDASI BT
Protocol Number: BTTC11-01
PI: [name] [name]
Protocol Acc #:

MD. Anderson Symptom Inventory (MDASI - BT)

Part I. How severe are your symptoms?

People with cancer frequently have symptoms that are caused by their disease or by their treatment. We ask to rate how severe the following symptoms have been in the last 24 hours. Please fill in the circle below from 0 (symptom has not been present) to 10 (the symptom was as bad as you can imagine it could be) for each item.

	Not Present	As Bad As You can Imagine									
	0	1	2	3	4	5	6	7	8	9	10
1. Your pain at its WORST?											
2. Your fatigue (tiredness) at its WORST?											
3. Your nausea at its WORST?											
4. Your disturbed sleep at its WORST?											
5. Your feeling of being distressed (upset) at its WORST?											
6. Your shortness of breath at its WORST?											
7. Your problem with remembering things at its WORST?											
8. Your problem with lack of appetite at its WORST?											
9. Your feeling drowsy (sleepy) at its WORST?											
10. Your having a dry mouth at its WORST?											
11. Your feeling sad at its WORST?											
12. Your vomiting at its WORST?											
13. Your numbness or tingling at its WORST?											
14. Your weakness on one side of the body at its WORST?											
15. Your difficulty understanding at its WORST?											
16. Your difficulty speaking (finding the words) at its WORST?											

Date: / /
(month) (Day) (Year)

Participant's Initials:

BTTC11-01 Patient #

PLEASE USE A BLACK INK PEN

MDASI BT
Protocol Number: BTTC11-01
PI: [name] [name]
Protocol Acc #:

	As Bad As You can Imagine										
	0	1	2	3	4	5	6	7	8	9	10
17. Your seizures at its WORST?											
18. Your difficulty concentrating at its WORST											
19. Your vision at its WORST?											
20. Your change in appearance at its WORST?											
21. Your change in bowel pattern (diarrhea or constipation) at its WORST											
22. Your irritability at its WORST?											

Part II. How have your symptoms interfered with your life?

Symptoms frequently interfere with how we feel and function. How much have your symptoms interfered with the following items in the last 24 hours:

	Interfered Completely										
	0	1	2	3	4	5	6	7	8	9	10
23. General activity?											
24. Mood ?											
25. Work (including work around the house) ?											
26. Relations with other people?											
27. Walking?											
28. Enjoyment of life ?											

Date: / /
(month) (Day) (Year)

MDASI BT

Protocol Number: BTTC11-01

Participant's Initials:

PI: [name] [name]

BTT C11-01 Patient #:

Protocol Acc #:

PLEASE USE A
BLACK INK PEN

MD. Anderson Symptom Inventory (MDASI - BT)

Participant
Signature

Date

Clinician
Signature

Date

17.4 Pill Diary Patient Initial: _____ BTTC ID #: _____ Bottle #: _____ Month #: _____

This calendar is for you to indicate that you took the drug(s) according to the instructions. Please put a check mark after each dose.

Please sign this calendar at the end of the cycle and bring the calendar and all study drug bottle(s) back to your next clinic visit.

DOSES: Lacosamide/Placebo _____ mg by mouth twice a day as close to 12 hours apart as possible.

Day 1 _____ _____ mg a.m. _____ p.m. _____	Day 2 _____ _____ mg a.m. _____ p.m. _____	Day 3 _____ _____ mg a.m. _____ p.m. _____	Day 4 _____ _____ mg a.m. _____ p.m. _____	Day 5 _____ _____ mg a.m. _____ p.m. _____	Day 6 _____ _____ mg a.m. _____ p.m. _____	Day 7 _____ _____ mg a.m. _____ p.m. _____	
Day 8 _____ _____ mg a.m. _____ p.m. _____	Day 9 _____ _____ mg a.m. _____ p.m. _____	Day 10 _____ _____ mg a.m. _____ p.m. _____	Day 11 _____ _____ mg a.m. _____ p.m. _____	Day 12 _____ _____ mg a.m. _____ p.m. _____	Day 13 _____ _____ mg a.m. _____ p.m. _____	Day 14 _____ _____ mg a.m. _____ p.m. _____	
Day 15 _____ _____ mg a.m. _____ p.m. _____	Day 16 _____ _____ mg a.m. _____ p.m. _____	Day 17 _____ _____ mg a.m. _____ p.m. _____	Day 18 _____ _____ mg a.m. _____ p.m. _____	Day 19 _____ _____ mg a.m. _____ p.m. _____	Day 20 _____ _____ mg a.m. _____ p.m. _____	Day 21 _____ _____ mg a.m. _____ p.m. _____	
Day 22 _____ _____ mg a.m. _____ p.m. _____	Day 23 _____ _____ mg a.m. _____ p.m. _____	Day 24 _____ _____ mg a.m. _____ p.m. _____	Day 25 _____ _____ mg a.m. _____ p.m. _____	Day 26 _____ _____ mg a.m. _____ p.m. _____	Day 27 _____ _____ mg a.m. _____ p.m. _____	Day 28 _____ _____ mg a.m. _____ p.m. _____	
		Patient Signature: _____				Date: _____	

PILL COUNT DOCUMENTATION:

TO BE COMPLETED BY CLINICAL RESEARCH STAFF

PATIENT INITIAL: _____ **BTTC I.D. #** _____ **Bottle #** _____ **MONTH #** _____

DOSE OF LACOSAMIDE PRESCRIBED: _____ **MG, PO**

LACOSAMIDE tablets are available in 50, 100, mg strengths. The study will provide drug adequate for 3 months of treatment.

XX

DATE DISPENSED: _____ (mm/dd/yy) **QUANTITY OF BOTTLES DISPENSED:** _____

QUANTITY OF 50 MG TABLETS DISPENSED: _____

QUANTITY OF 100 MG TABLETS DISPENSED: _____

NUMBER OF _____ **MG TABLETS PER DAY REQUIRED TO ACHIEVE PRESCRIBED DOSE:** _____

XX

